If the participant does not have a smart phone, we will use the WatchPAT 200 device (Itamar Medical, Ltd) that we are currently using in two clinical trials approved by the VA IRB. This non-disposable device also has a chest and a finger sensor. Data are stored in the device, rather than transmitted to an Itamar server. Participants will mail the WatchPAT 200 back to the research office in a FEDEX box that the study will provide. Test data are then downloaded onto a study computer and stored on the VA HSR&D CSHIIP server.

Baseline Visit 1 (30-45 minutes)

1. Research staff administer baseline questionnaires part 1 using VVC
 - o Demographic questions
 - o Mini-mental State Examination (MMSE)
 - o Self-administered comorbidity index
 - o Primary Care PTSD Screen
 - o Generalized Anxiety Disorder-7
 - o Insomnia Severity Index
 - o Restless Leg Syndrome Questionnaire
 - o Self-efficacy Measure for Sleep Apnea
 - o Behavioral Determinants of PAP Adherence questionnaire
2. Research staff explain how to complete the sleep diary
3. Research staff explain how to use the home sleep apnea testing, if necessary

Baseline Visit 2 (30 minutes)

1. Research staff administer baseline questionnaires part 2 using VVC
 - o Pittsburgh Sleep Quality Index
 - o Epworth Sleepiness Scale
 - o Nocturia questions
 - o Functional Outcomes of Sleep Questionnaire-10
 - o PROMIS-29 questionnaire

Pre-randomization review

Participant's baseline assessment results will be reviewed during a weekly investigators' meeting to determine eligibility for randomization. The meeting will include a study physician ([name] and/or [name], who are both certified in Internal Medicine, Geriatric Medicine and Sleep Medicine), a psychologist specializing in Behavioral Sleep Medicine ([name] and/or [name]), and a member of the study team who completed baseline assessments. These investigators and study team member will review the baseline assessment and medical record to determine if a participant meets the inclusion criteria for randomization and does not meet any of the exclusionary criteria that would make them ineligible for randomization.

Participants will be excluded if any of the following are present:

- repeat home sleep apnea testing result AHI is < 15
- Mini-Mental State Examination (MMSE) score < 24 the participant has current, significant psychopathology (e.g., active psychosis)
- the participant has severe unstable medical illness

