Participants with stable psychiatric/medical conditions, and those using medications for sleep will not be excluded.

Randomization

Participants will be randomized following guidelines of the Consolidated Standards of Reporting Trials (CONSORT). Stratified randomization will be used based on (stratum 1) any PAP use over the prior 12 months, versus (stratum 2) no PAP use over the prior 12 months, since this may predict treatment response. Within each stratum, randomization sequences will be "blocked" using a block size of n=4. The statistician will generate the stratified randomization sequence prior to study onset and it will be transferred to a series of "security envelopes" by another staff member (independent from the study) and stored in a secure location. Once eligibility is determined, another staff person (independent from the study) will open the next envelope in sequence within the appropriate stratum (i.e., for random allocation concealment). Participants will be randomized to the active intervention (i.e., behavioral intervention to improve PAP use) or the general sleep education control condition.

Intervention and control groups

The structure of the intervention and control conditions is identical. Participants in both groups will attend 5 VVC sessions over the course of 8 weeks, plus monthly follow-up telephone contacts for 4 additional months. The content of the two conditions is different and is explained in the tables below. Between session 1 and session 2 of the intervention and control conditions, participants (in both groups) who do not currently have a PAP device, or do not have the current PAP model dispensed by the Sleep Medicine clinic, will receive a new PAP device, alongwith new masks and tubing. To avoid delays in receiving the PAP device from the Sleep Medicine clinic, [name] (Clinic Director) has agreed that one of the research staff ([name]) a certified respiratory technician, can dispense the new PAP machine to the research participant. [name] will set-up the PAP according to the pressure prescription provided by a Sleep Medicine provider and will connect the modem for remote monitoring by Sleep Clinic staff as part of usual care. [name] has also given permission for [name] and the interventionists to access the clinic data so summary PAP usage reports can be obtained.

Note: No recalled Philip Respironics PAP devices will be dispensed to study subjects.

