Each of these assessments were observed at four time points: baseline, post-treatment, six-month follow-up, and at twelve-month follow-up. Each outcome, at each of the four timepoints, was analyzed using a two-level mixed-effects analyses, time nested within person, with a fixed intercept. For each outcome, we considered three possible residual covariance matrix structures -- unstructured, autoregressive, and exchangeable. The structure providing the best fit (lowest BIC) was selected. The autoregressive residual structure had the smallest BIC for three outcomes, PSQI Total score, PSQI Factor 1, and Promis29-MH. The exchangeable structure had the lowest BIC for the other five assessment outcomes (PSQI Factor 2, PSQI Factor 3, ESS, FOSQ-10, and Promis29-PH). We modeled each assessment outcome as a function of treatment group (coded 1=treatment, 2=control), time (treated categorically, coded 1=Baseline, 2=Post-Treatment, 3=Six-month follow-up, 4=Twelve-month follow-up), and the treatment by time interaction. For each combination of group by month, we estimated the mean and 95% Confidence interval. The treatment effect at six-month follow-up was assessed via an interaction contrast by applying the contrast coefficients (-1 1) to treatment group and the contrast coefficients (-1 0 1 0) to time, and interacting these contrasts. Similarly, the treatment effect at twelve-month follow-up was assessed by applying the contrast coefficients (-1 0 0 1) to time and interacting that contrast with the contrast on group. All assessment outcomes were double data entered, and all discrepancies were resolved by consulting original data forms and correcting the erroneous data entry. This was iteratively repeated until all discrepancies between the original and "double punched" datasets were eliminated.

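### Aims 2 and 3: the change-from-baseline contrast with a separate baseline mean per arm is valid, but a common-baseline model would usually be more precise on data already collected

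*Combined protocol and SAP*

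**What the plan says.** The analysis is set out under Data Analysis, Aims 2 and 3. Baseline is treated as a response: "Each of these assessments were observed at four time points: baseline, post-treatment, six-month follow-up, and at twelve-month follow-up". The model has group, categorical time ("4=Twelve-month follow-up), and the treatment by time interaction") and no constraint on the baseline means. The baseline score is not used as a covariate.

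The 6-month effect is defined as follows: "The treatment effect at six-month follow-up was assessed via an interaction contrast by applying the contrast coefficients (-1 1) to treatment group", crossed with time coefficients that set month 6 against baseline. The 12-month effect is formed in the same way, by "applying the contrast coefficients (-1 0 0 1) to time".

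Two covariance structures are in use, chosen by BIC. On the first the plan says: "The autoregressive residual structure had the smallest BIC for three outcomes, PSQI Total score, PSQI Factor 1, and Promis29-MH". For the remaining scores (PSQI Factors 2 and 3, ESS, FOSQ-10 and PROMIS-29 Physical Health) an exchangeable structure was preferred.

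On timing, PSQI, ESS, FOSQ-10 and PROMIS-29 are listed under Baseline Visit 2. Under Pre-randomization review, the investigators then "review the baseline assessment and medical record to determine if a participant meets the inclusion criteria for randomization". Allocation follows, under Randomization: "Once eligibility is determined, another staff person (independent from the study) will open the next envelope in sequence within the appropriate stratum".

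**The concern.** Two groups by four visits gives eight free means, one of which is spent on a baseline difference between arms. Because baseline is measured before allocation, that difference is zero in expectation by design. The stated contrast nevertheless estimates it and subtracts it, so its sampling error enters the treatment effect. A model with one baseline mean shared by both arms (seven means) targets the same effect without that component.

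What is at stake is the width of the confidence intervals for the secondary and exploratory outcomes. These are the outcomes for which the Sample Size table lists 106 participants, against 90 for PAP use. The baseline scores are already collected, so any gain needs no further participants.

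**Working it through.** **Inputs from the documents.** 106 randomized and 20% attrition for questionnaires (Sample Size); four visits, eight cell means, the two contrasts and the two covariance structures (Data Analysis, Aims 2 and 3).

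**Assumptions.** 53 per arm (there are two arms in blocks of four, but the ratio is not stated); equal variance σ² at every visit; dropout unrelated to outcome; covariance treated as known; a range for the correlation ρ between baseline and the visit in question, which the documents do not give.

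**The plan's own figure.** FOSQ is the only questionnaire row in the power table that can be recomputed without an unstated SD. With d = 0.64 and an assumed two-sided 5% t-test, 42 per arm (0.8 × 53 = 42.4) gives power 0.826 and 40 per arm gives 0.807, against 0.806 stated. The row is roughly reproduced. It does not say whether d is scaled to follow-up scores or to change scores, so it gives no information about ρ and is not used below.

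**Step 1: exchangeable, complete data, n per arm.**
- Free baseline means: variance = 4σ²(1−ρ)/n.
- Common baseline mean: variance = 2σ²(1−ρ²)/n.
- Ratio = (1+ρ)/2, so the reduction is (1−ρ)/2.
- Example, ρ = 0.5, n = 53: 4 × 0.5/53 = 0.0377σ² against 2 × 0.75/53 = 0.0283σ², a reduction of 25%.

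**Step 2: exchangeable, fraction f followed, the rest with baseline only.**
- Free: 2σ²[(1−ρ²)/(53f) + (1−ρ)²/53]. Common: 2σ²(1−ρ²)/(53f).
- Reduction = f(1−ρ)/[(1+ρ) + f(1−ρ)].
- With f = 0.8: ρ = 0.3 gives 0.56/1.86 = 30.1%; ρ = 0.5 gives 0.40/1.90 = 21.1%; ρ = 0.9 gives 0.08/1.98 = 4.0%.

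The last row of the table was computed by generalised least squares over the four visits. The figures are the same at 6 and 12 months.

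| Exchangeable, variance reduction | ρ=0.3 | 0.5 | 0.7 | 0.8 | 0.9 |
|---|---|---|---|---|---|
| Complete data | 35.0% | 25.0% | 15.0% | 10.0% | 5.0% |
| 20% with baseline only | 30.1% | 21.1% | 12.4% | 8.2% | 4.0% |
| 20% leaving after post-treatment | 30.3% | 21.4% | 12.8% | 8.5% | 4.2% |

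Interval width falls by 1 − √(1 − reduction). That is 19, 13, 8, 5 and 3% with complete data, and 16, 11, 6, 4 and 2% with baseline-only dropout.

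**Step 3: autoregressive by visit order, lag-1 correlation r.** The correlation with baseline is r² at 6 months and r³ at 12 months, and the same formulas apply. Example, r = 0.5 at 6 months with f = 0.8: ρ = 0.25, so 0.60/1.85 = 32.4%.

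| Autoregressive, variance reduction (6 months / 12 months) | r=0.5 | 0.7 | 0.9 |
|---|---|---|---|
| Complete data | 37.5 / 43.8% | 25.5 / 32.8% | 9.5 / 13.6% |
| 20% with baseline only | 32.4 / 38.4% | 21.5 / 28.1% | 7.7 / 11.1% |
| 20% leaving after post-treatment | 33.3 / 38.6% | 22.7 / 28.7% | 8.4 / 11.7% |

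**Step 4: relaxing equal variances (complete data).** With baseline SD s₀ and follow-up SD s₁, the reduction is (s₀ − ρs₁)²/(s₀² + s₁² − 2ρs₀s₁). The SD ratios s₁/s₀ below are assumptions.
- ρ = 0.7, ratio 1.2: 0.0256/0.76 = 3.4%.
- ρ = 0.8, ratio 1.2: 0.0016/0.52 = 0.3%.
- ρ = 0.7, ratio 0.8: 0.1936/0.52 = 37.2%.

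**Step 5: finite-sample check.** In 20,000 simulated trials of 106 participants, with the baseline slope estimated, the reduction was 34.6, 19.5 and 4.5% at ρ = 0.3, 0.6 and 0.9 (formula: 35, 20, 5%). Both estimators were centred on zero when there was no effect.

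**The case against.** The strongest reply is that nothing here is an error. A group-by-time contrast on change is standard and fully specified, and it suits an aim framed as improvement. That stands: the point is about efficiency between two valid estimators.

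The second reply is that the size rests on a correlation the documents do not give, and on equal visit variances. This also stands. Both covariance structures chosen normally imply equal variances, which lends some support, but selection by BIC does not prove it. The lower ends of the ranges are therefore not floors, as Step 4 shows.

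The third reply is that the opportunity may have passed. Enrollment reached 106, the analysis text is in the past tense, and the covariance structures had already been selected. This stands in part. A post hoc model can only support the stated contrast, so the gain reaches the trial's conclusions only if the change is made before results by arm are known. The documents do not say whether arm-level results have been seen, so the fix is conditional.

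A reader might infer that the contrast is biased by chance baseline imbalance, that the questionnaire outcomes are underpowered, or that the increase from 90 to 106 was unnecessary. The documents support none of these. Randomization makes the contrast unbiased, and without the SDs, their scale, alpha and ρ, no shortfall or excess against the stated power can be shown.

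**Conclusion.** The point holds as an optional gain in precision for the eight secondary and exploratory questionnaire scores. With equal visit variances and 20% attrition, a common baseline mean lowers the variance of the effect by about 4-30% for the five exchangeable outcomes (assumed ρ 0.9-0.3; 5-35% with complete data). For PSQI Total, PSQI Factor 1 and PROMIS-29 Mental Health, the reduction is about 8-33% at 6 months and 11-39% at 12 months (assumed lag-1 correlation 0.9-0.5). The gain can be close to zero when ρ is high and the follow-up SD exceeds the baseline SD. The stated contrast remains valid, and the Aim 1 comparison of PAP use is not touched.

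**What to change.** In Data Analysis, Aims 2 and 3, fit the same repeated-measures model, with the same covariance structure and the same participants, but with one baseline mean common to both arms. Take the treatment-minus-control difference at 6 and 12 months as the effect. State the direction, because the present group coding (1 = treatment, 2 = control) with coefficients (-1 1) yields control minus treatment.

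- If outcomes have not been analysed by arm, make this the Aim 2/3 analysis by dated amendment.
- If they have, keep the stated contrast as the main result. Report the common-baseline estimates and confidence intervals beside it, labelled post hoc, and do not present them as 16 further tests (eight outcomes at two visits).

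In either case, report the estimated correlation with baseline for each outcome and visit, so that the reader can see whether the gain mattered.

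The cost is a short change to the text and one extra model for each of the eight outcomes, with no new data. If the model is post hoc, its status is supportive only.

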STUDY PROTOCOL

Project title: Addressing Insufficient Positive Airway Pressure Use Among Older Veterans With Obstructive Sleep Apnea (IIR 20-046)

PI: [name]

SPECIFIC AIMS

Primary Aim 1: Test the efficacy of a novel program for improving PAP usage, compared to a general sleep education attention control program, among middle-aged and older Veterans with previously diagnosed OSA who have insufficient PAP use.

- Hypothesis 1a: Compared to control, Veterans who receive the intervention will have greater objectively measured PAP use (mean hours of PAP use per night) at 6-months follow-up.
- Hypothesis 1b: Effects will be sustained at 12-months follow-up.

Secondary Aim 2: Test the efficacy of this novel program for improving sleep quality, daytime sleepiness and sleep-related function compared to the control program.

- Hypothesis 2a: Compared to control, Veterans who receive the intervention will report better sleep quality (PSQI), less daytime sleepiness (ESS), and better sleep-related function (FOSQ-10) at 6-months follow-up.
- Hypothesis 2b: Effects will be sustained at 12-months follow-up.

Exploratory Aim 3: Test the efficacy of this novel program for improving health-related quality of life compared to the control program.

- Hypothesis 3a: Compared to control, Veterans who receive the intervention will report better health-related quality of life (PROMIS-29 v2.1 Physical and Mental Health Summary Scores) at 6-months follow-up.
- Hypothesis 3b: Effects will be sustained at 12-months follow-up.

RESEARCH DESIGN AND METHODS

Basic Study Design

This is a 4-year, randomized controlled trial testing a novel intervention for older Veterans (aged ≥ 50 years) with previously diagnosed OSA, who were prescribed PAP therapy but have insufficient PAP use (defined as no use or use that does not meet Medicare standards). The intervention involves a structured, supervised approach (with weekly oversight by telephone with a study psychologist) that can be provided by individuals from various disciplines to maximize future implementation. The intervention is 6 months in duration, with sessions at weeks 1,2,3,4 and 8, and brief follow-up sessions at 12,16, 20, and 24 weeks. Core components of the intervention include:

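### Do hypotheses 2b and 3b go untested because no 6-to-12-month contrast is described?

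*Combined protocol and SAP*

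**What the plan says.** Specific Aims states "Hypothesis 2b: Effects will be sustained at 12-months follow-up" for PSQI, ESS and FOSQ-10, and "Hypothesis 3b: Effects will be sustained at 12-months follow-up" for the PROMIS-29 summary scores. Neither hypothesis defines the word or sets a retention margin.

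Data Analysis, Aims 2 and 3, fits one mixed model per outcome, with group, categorical time (four visits) and their interaction. The 6-month effect comes from "applying the contrast coefficients (-1 1) to treatment group and the contrast coefficients (-1 0 1 0) to time". For month 12, "the treatment effect at twelve-month follow-up was assessed by applying the contrast coefficients (-1 0 0 1) to time", again crossed with group. The section adds: "For each combination of group by month, we estimated the mean and 95% Confidence interval". The residual structure is autoregressive for three outcomes, PSQI Total among them ("The autoregressive residual structure had the smallest BIC for three outcomes, PSQI Total score, PSQI Factor 1, and Promis29-MH"), and exchangeable for the rest ("The exchangeable structure had the lowest BIC for the other five assessment outcomes").

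No between-group contrast from month 6 to month 12 is described.

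**The concern.** *Sustained* suggests a comparison over time: a benefit existed at 6 months and had not faded by 12. Both planned contrasts start from baseline, and the later one ignores month 6. A significant 12-month result could therefore follow either a fully kept or a shrunken benefit, and a non-significant one could follow a benefit that was fully kept. The described confidence intervals belong to the group-by-visit means, and a reader cannot combine them into an interval for the change in effect, because that also needs the within-person covariance. If the hypotheses were about the share of benefit kept, the plan would offer no estimate of it with its uncertainty.

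**Working it through.** **1. What each contrast estimates.** Group is coded 1 = treatment, 2 = control, so (-1 1) gives control minus treatment. Write D0, D6 and D12 for that difference in means at baseline, 6 and 12 months.

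- 6-month contrast: D6 − D0
- 12-month contrast: D12 − D0
- 12-month minus 6-month: (-1 0 0 1) − (-1 0 1 0) = (0 0 -1 1), that is D12 − D6

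The 12-month contrast tests whether the groups' changes from baseline differ at 12 months. Under Basic Study Design the last intervention contact is at week 24, so it asks whether a benefit is present about six months after contact ends. That is the ordinary sense of *sustained*. The point estimate of D12 − D6 already follows from the group-by-visit means. Only its interval is not described.

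**2. Inputs for the size of the gap.**

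- Sample Size: 106 randomized and 20% attrition; 106 × 0.8 = 84.8, taken as 85 (42 and 43).
- Sample Size: PSQI difference 2.5 points, power 0.803.
- Assumed: two-sided 5% level; visits equally spaced in the autoregressive structure; adjacent-visit correlation r from 0.3 to 0.7. The documents give no correlation.

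With 83 degrees of freedom t = 1.989, and k = √(1/42 + 1/43) = 0.217. Noncentral-t power of 0.803 requires d = 0.617, so SD = 2.5 / 0.617 = 4.05. As a check on the method, FOSQ-10 at d = 0.64 gives 0.830 here, 0.826 at 42 per arm and 0.807 at 40 per arm, against the stated 0.806. The method is close to the plan's but not identical.

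The documents do not say whether this SD is for a single visit or for the 6-month change. Both readings are shown.

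**3. Precision of D12 − D6.** Half-width = t × SD(visit) × √(2(1 − r)) × k. The two visits are adjacent, so this form serves both structures.

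- Single-visit reading: 1.989 × 4.05 × 0.217 = 1.75, times √(2(1 − r)). At r = 0.3: 1.75 × 1.183 = 2.07. At r = 0.7: 1.75 × 0.775 = 1.35.
- Change reading, autoregressive: SD(visit) = 4.05 / √(2(1 − r²)), so the half-width is 1.75 / √(1 + r). At r = 0.3: 1.53. At r = 0.7: 1.34.
- Change reading, exchangeable: 1.75 at every r.

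PSQI Total is autoregressive, so the exchangeable value stands for an outcome with similar stated power, such as FOSQ-10. Losing half of 2.5 points is 1.25 points, which is less than every half-width above. Power to detect that loss is 22 to 45% across all these cases.

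**4. What the planned 12-month contrast already shows.** Take the change reading, which reproduces the stated 6-month power. Given a favourable significant 6-month result, the probability of a significant 12-month contrast (bivariate normal; autoregressive and exchangeable together) is:

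| Benefit kept at 12 months | Probability |
|---|---|
| All | 81–86% |
| Three quarters | 55–63% |
| Half | 29–34% |

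The planned test therefore responds strongly to loss of benefit, although one test result cannot measure that loss.

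**The case for a change.** The best case for the concern is that two significance results are a poor guide to retention. From the table, 14 to 19% of trials with a fully kept benefit would miss significance at 12 months, and 29 to 34% would reach it after losing half. An example at 42 per arm, exchangeable, r = 0.5: the standard error of either contrast is √((2/42) × 2 × 0.5) = 0.218 SD. An effect falling from d = 0.64 to 0.43 still gives z = 0.43 / 0.218 = 1.97. The 95% interval for the change, −0.21 ± 1.96 × 0.218, runs from −0.64 to +0.22 and so includes loss of the whole effect. The extra contrast costs nothing, since the models are already fitted.

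All of this is correct, and it shows that *how much was kept* is a different question from *is it still there*. It does not show that the plan asks the first one. Basic Study Design lists the secondary measures at 6 and 12 months with no comparison between the two. It speaks of maintenance only for PAP use, and there too as something tested at 12 months.

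The added interval would also rarely settle retention. It becomes narrower than 1.25 points only under favourable assumptions: at r = 0.8 on the single-visit reading it is about 1.1 points (42 per arm). That the plan does not mention standard errors for the contrasts is weak evidence that they will be withheld, since a tested contrast has one.

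**Conclusion.** There is no error here. Hypotheses 2b and 3b are tested by a contrast that matches their ordinary meaning, and following the plan gives a sound answer to the question it sets. What remains is an undefined word and an estimate that a reader might like to see. At r from 0.3 to 0.7 that estimate would carry a half-width of 1.34 to 2.07 PSQI points, or 1.34 to 1.53 in the case that best fits PSQI Total (autregressive structure, change reading). No planned test, power figure or sample size changes.

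The conclusion rests on reading *sustained* as *present at 12 months*. The plan supports this by setting no margin and making no comparison of month 12 with month 6. The numerical illustration also depends on the assumed correlations, the 42/43 split and the back-calculated SD, but the conclusion does not. It covers Aims 2 and 3 only. Hypothesis 1b on PAP use is a separate matter.
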